12.7 SERIOUS ADVERSE EVENTS

12.7.1 Definitions of Serious Adverse Events

The definitions of serious adverse events (SAEs) are given below. The principal investigator is responsible for ensuring that all staff involved in the trial is familiar with the content of this section.

An SAE or reaction is defined as any untoward medical occurrence that:

- results in death, is immediately life-threatening,
- requires at least a 24-hour inpatient hospitalization or prolongation of existing hospitalization,
- results in persistent or significant disability/incapacity,
- causes a congenital anomaly/birth defect.

Medical and scientific judgment should be exercised in deciding whether expedited reporting is appropriate in other situations, such as important medical events that may not be immediately life-threatening or result in death or hospitalization, but may jeopardize the subject or may require

intervention to prevent one of the other outcomes listed in the previous definition. These should also usually be considered serious. Examples of such events are intensive treatment in an emergency room or at home for allergic bronchospasm; blood dyscrasias or convulsions that do not result in hospitalization; or development of drug dependency or drug abuse. Death due to disease progression will be recorded on the CRF. A SUSAR is defined as a suspected unexpected SAE, and SUSAR reporting is encompassed within SAE reporting guidelines as defined in this section.

Treatment within or admission to the following facilities is not considered to meet the criteria of “inpatient hospitalization” (although if any other SAE criteria are met, the event must still be treated as an SAE and immediately reported):

- Emergency Department or Emergency Room
- Outpatient or same-day surgery units
- Observation or short-stay unit
- Rehabilitation facility
- Hospice or skilled nursing facility
- Nursing homes, Custodial care or Respite care facility

Hospitalization during the trial for a pre-planned surgical or medical procedure (one which was planned prior to entry in the trial) does not require reporting as a serious adverse event to the Sponsor ([name]).

12.7.2 Serious Adverse Event Reporting by Investigators

It is important to distinguish between “serious” and “severe” adverse events, as the terms are not synonymous. Severity is a measure of intensity; however, an AE of severe intensity need not necessarily be considered serious. For example, nausea, which persists for several hours, may be considered severe nausea, but may not be considered an SAE. On the other hand, a stroke which results in only a limited degree of disability may be considered only a mild stroke, but would be considered an SAE. Severity and seriousness should be independently assessed when recording AEs and SAEs on the CRF.

Adverse events classified by the treating investigator as **serious** require expeditious handling and reporting to the IRB or other regulatory agencies in order to comply with regulatory requirements. Serious adverse events may occur at any time from the signing of the informed consent form through the 9-month follow-up period after the last trial treatment. Sponsor or designee must be notified of all SAEs, regardless of causality, within 24 hours of the first knowledge of the event by the treating physician or research personnel.

To report an SAE, see the appropriate SAE CRF page.

All SAEs and medically confirmed deaths (regardless of causality assessment) occurring on trial treatment or within 30 days of last trial treatment must be reported to the TG Therapeutics, the Johns Hopkins IRB and the Chair of the DSMB as SAEs within the CRF and followed until resolution (with autopsy report if applicable).

Deaths occurring within 30 days after last trial treatment that are deemed ‘possibly’ or ‘probably’ related to ublituximab must be reported as SAEs within the CRF (with an autopsy report if available).

Deaths occurring within 30 days after last trial treatment and not attributed to trial treatment (e.g., disease progression) need not be reported in an expeditious manner to the TG Therapeutics and the Chair of the DSMB, but can simply be captured on the appropriate CRF as an SAE (death). The Johns Hopkins IRB should be notified as soon as possible.

The investigator must review and sign off on the SAE data on the SAE report. The SAE will be reported to the Sponsor (or Sponsor designee) as outlined in the Safety Monitoring Plan.

If an SAE is reported to the sponsor or designee via fax, the same information must be entered on the CRF within 24 hours (1 business day). Transmission of the SAE report should be confirmed by the site personnel submitting the report.

Follow-up information for SAEs and information on non-serious AEs that become serious should also be reported to the sponsor or designee as soon as it is available; these reports should be submitted using the appropriate CRF. The detailed SAE reporting process will be provided to the sites in the Safety Monitoring Plan.

Investigators must report SAEs and follow-up information to their responsible Institutional Review Board (IRBs)/Independent Ethics Committee according to the policies of the responsible IRB (Research Ethics Committee).

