12.4 PROTOCOL-SPECIFIC EXPEDITED ADVERSE EVENT REPORTING EXCLUSIONS

There are no exclusions for expedited adverse event reporting. All adverse events, including death, will be considered unexpected and subject to expedited reporting.

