12.11.3 Deaths

Deaths that occur during the protocol-specified AE reporting period that are attributed by the investigator for up to 30 days post the dose of trial drug will be recorded on the appropriate trial CRF. All on-trial deaths, regardless of attribution, will be expeditiously reported to the TG Therapeutics and to the Johns Hopkins IRB.

When recording a serious adverse event with an outcome of death, the event or condition that caused or contributed to the fatal outcome will be recorded as the single medical concept on the Adverse Event page of the CRF. If the cause of death is unknown and cannot be ascertained at the time of reporting, "Death NOS" will be recorded on the CRF Adverse Event page.

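### Section 12.7.2 waives prompt notice to the DSMB Chair of deaths judged unrelated, contradicting the 24-hour rule of Section 12.6.1 and the no-exclusions rule of Section 12.4

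*Combined protocol and SAP*

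**What the plan says.** All references are to the combined protocol and SAP.

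- **Section 12.7.2, the exemption.** Deaths in the 30 days after the last trial treatment that are not attributed to it "need not be reported in an expeditious manner to the TG Therapeutics and the Chair of the DSMB". Entry on the CRF as an SAE is enough for these two recipients. The IRB is to be told as soon as possible.
- **Section 12.7.2, earlier paragraphs.** "All SAEs and medically confirmed deaths (regardless of causality assessment) occurring on trial treatment or within 30 days of last trial treatment must be reported", with recipients that include "the Johns Hopkins IRB and the Chair of the DSMB as SAEs within the CRF and followed until resolution". Separately, "Sponsor or designee must be notified of all SAEs, regardless of causality, within 24 hours of the first knowledge of the event".
- **Section 12.6.1.** A serious adverse event goes to TG Therapeutics and the DSMB Chair as soon as possible, and in no more than 24 hours.
- **Section 12.7.1.** An event that results in death is an SAE.
- **Section 12.4.** "There are no exclusions for expedited adverse event reporting", followed by "All adverse events, including death, will be considered unexpected and subject to expedited reporting".
- **Section 12.11.3.** "All on-trial deaths, regardless of attribution, will be expeditiously reported to the TG Therapeutics and to the Johns Hopkins IRB". The DSMB is not named.
- **Sections 4.1 and 13.** The DSMB reviews safety after the first two subjects or at six months, whichever comes first. Enrolment is held until it has reported. Section 4.1 adds a meeting once the next three subjects have been infused. Section 13 adds a final review and a six-monthly trigger.

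**The concern.** The same death falls under two incompatible instructions. One sends it to the DSMB Chair within a day. The other says prompt notice to the Chair is unnecessary if the investigator judges the death unrelated. The exemption is the more specific text on deaths, so it is likely to be the one followed.

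What is at stake is the DSMB's ability to act while subjects are still being dosed. Section 13, headed as stopping rules, sets no numerical threshold and leaves the decision to the DSMB's view of the safety data. The events it lists for DSMB attention are neutropenia, thrombocytopenia, infection and liver enzyme elevation; death is not listed separately.

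Attribution is also hard in this setting. Subjects receive high-dose steroids, and the synopsis says about half have historically needed plasma exchange. Section 1.1 gives plasma exchange a 4–10% risk of line infection or thrombotic complications. A fatal infection could reasonably be put down to one of these, yet infection is an event the DSMB is charged with following.

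**Working it through.** There is no figure in the plan to reproduce. The check compares the rules and then follows enrolment to see who could be infused before the DSMB knows.

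**Step 1: the rules side by side.** Take a death within 30 days of the infusion that the investigator judges unrelated.

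| Section | Recipient | Time limit | Conflict with the exemption |
|---|---|---|---|
| 12.7.2, exemption | TG Therapeutics and DSMB Chair | None; CRF entry is enough | – |
| 12.6.1 with 12.7.1 | TG Therapeutics and DSMB Chair | 24 hours | Direct, on timing and on both recipients |
| 12.4 | Not named | Expedited, no exclusions | Direct, on whether any exemption may exist |
| 12.7.2, earlier paragraph | TG Therapeutics, IRB and DSMB Chair | None stated | Partial: it reports regardless of causality, but without a deadline |
| 12.11.3 | TG Therapeutics and IRB | Expeditious | TG Therapeutics only; silent on the DSMB |

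Section 12.6.1 carries the argument because it alone names the DSMB Chair and also sets a time limit. Its recording window runs from consent to 30 days after treatment, so every exempted death lies inside it.

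**Step 2: who else hears promptly.** The IRB is told as soon as possible, and the sponsor within 24 hours. The sponsor is the investigator (synopsis; Section 16.3), so the sponsor notice may not go beyond the person who judged causality. The exemption removes prompt notice to the two outside recipients: the DSMB Chair, and TG Therapeutics, which takes on monitoring under Section 14.1.

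**Step 3: who could be infused before the DSMB knows.** Five subjects are planned, with a DSMB hold after the first two.

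- Subject 1 dies before the hold: subject 2 could be infused, so 2 − 1 = 1 further subject.
- Subject 1 or 2 dies after the first DSMB review but within 30 days of infusion: subjects 3 to 5 could be infused, so 5 − 2 = 3.
- Subject 3 dies: subjects 4 and 5, so 5 − 3 = 2.
- Subject 4 dies: subject 5, so 5 − 4 = 1.
- Subject 5 dies: none.

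The range is 0 to 3 further subjects. These are upper limits, since a six-month DSMB review could fall in between.

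**Step 4: scale.** One death would be 1/5 = 20% of the sample. This shows how much one event weighs in the DSMB's data. It does not measure the effect of the delay, because the death is recorded as an SAE under either rule.

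**The case against.** The strongest reply is that the safeguard already exists. Section 12.6.1 gives the DSMB Chair 24-hour notice. The exemption covers only deaths within 30 days that are judged unrelated. The IRB and the sponsor are still told, and Section 4.1 bars further enrolment after two subjects until the DSMB has reported. Section 12.7.2 also leaves the detailed SAE process to a Safety Monitoring Plan, and Section 4.1 cites a DSMB charter; either might settle notice to the Chair. All of this limits the exposure. None of it removes the contradiction: the hold does not protect subject 2 or the later subjects among 3 to 5, and documents outside the protocol do not cure two conflicting instructions within it.

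The paragraphs of Section 12.7.2 can also be partly reconciled. Both record the death as an SAE on the CRF, and the earlier one sets no deadline. That stands, and it is why the case rests on Sections 12.6.1 and 12.4.

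A reader might infer three stronger things that the documents do not support:

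- *That each of Sections 12.4, 12.7.2 (earlier paragraph) and 12.11.3 requires prompt notice to the DSMB Chair.* None does by itself: the first names no recipient, the second gives no time limit, and the third omits the DSMB.
- *That the DSMB would be left unaware for months.* The interval depends on enrolment speed, which is not given.
- *That the death would go uncounted.* It is entered on the CRF as an SAE, and the synopsis has the DSMB review the recorded data.

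**Conclusion.** The contradiction is real and stands in the current text. Section 12.7.2 cannot be followed together with Section 12.6.1, and Section 12.4 rules out the kind of exclusion it creates. The conflict with Section 12.11.3 concerns TG Therapeutics only; that section's own gap is that it leaves out the DSMB.

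The consequence is conditional. If a subject dies within 30 days, the death is judged unrelated, and staff follow the exemption, then up to three further subjects could be infused before the DSMB knows. This assumes that no six-month review falls in between, that nobody informs the Chair voluntarily, and that the Safety Monitoring Plan and DSMB charter do not say otherwise. The length of the delay cannot be stated from the documents. This is an internal inconsistency that should be corrected; it does not show that the trial lacks a reporting safeguard.

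**What to change.** 1. Delete the exemption paragraph in Section 12.7.2.
2. In its place, state that the 24-hour rule of Section 12.6.1 applies to every death on treatment or within 30 days, regardless of attribution.
3. Add the DSMB Chair to the recipients in Section 12.11.3.

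The Safety Monitoring Plan and DSMB charter should be checked against the amended text. The 30-day window should be written out, because Section 12.7.2 also refers to SAEs through the 9-month follow-up while Section 12.6.3 limits reporting after 30 days to related events.

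The cost is two sentences and, at one death per subject at most, no more than 5 × 1 = 5 reports. No analysis, sample size or visit changes.

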12.8 SPONSOR SAE REPORTING REQUIREMENTS

The Sponsor ([name]) with assistance from TG Therapeutics are responsible for reporting relevant SAEs to the competent authority, other applicable regulatory authorities, and participating investigators, in accordance with ICH guidelines, FDA regulations, and/or local regulatory requirements.

The Sponsor ([name]) with assistance from TG Therapeutics are responsible for reporting unexpected fatal or life-threatening events associated with the use of the trial drug to the regulatory agencies and competent authorities via telephone or fax within 7 calendar days after being notified of the event. The Sponsor will report all related but unexpected SAEs including non-death/non-life-threatening related but unexpected SAEs associated with the use of the trial medication to TG Therapeutics and the Johns Hopkins IRBs by safety report within 14 calendar days of notification. TG Therapeutics is required to notify the FDA.

12.9 RECORDING OF ADVERSE EVENTS AND SERIOUS ADVERSE EVENTS

Investigators will use correct medical terminology/concepts when recording AEs or SAEs on the SAE Report Forms and AE CRF. Colloquialisms and abbreviations will be avoided.

All AEs, including those that meet SAE reporting criteria, will be recorded on the AE CRF; AEs that meet the definition of an SAE will additionally be reported following the procedures noted in Section 14.7.

12.10 IMMUNOGENICITY AND PHARMACOKINETICS

12.10.1 Pharmacokinetic (PK) Sampling:

Patients will have pharmacokinetic (PK) sampling (serum) performed as noted on the schedule below:

Time point
Pre-dose
1 min prior to EOI
30 min post EOI ¹
6 hour post EOI ²

24 hour post EOI ³
72 hour post EOI ³
168 hour post EOI ³

EOI: End of Infusion

¹ +/- 5 minutes

² +/- 30 minutes

³ +/- 2 hours

PK Sampling Procedures - IMPORTANT

Stop and start times of UTX infusion must be recorded and actual time/dates of samples drawn must be provided. The subject will not receive any additional infusions of ublituximab.

All samples to be obtained for PK analysis of ublituximab will be serum. One 6-ml blood sample is required for each sample time point.

After centrifugation, 2 aliquots of 0.5 ml of serum should be stored at -20°C to 70°C at the site. One aliquot will be sent to TG Therapeutics and the second aliquot will be shipped to TG Therapeutics after the first sample is received by them. All samples must be sent within 14 days of being collected from the subject.

Approximately seven (7) samples over 7 days should be collected for the PK analysis of ublituximab.

12.10.2 PK Sample Collection and Processing:

- a. Peripheral blood is to be drawn into heparinized vacutainer tubes. The patient's initials, time sample obtained, and date sample was obtained should be recorded on each tube as well as on the respective PK timesheet in the CRF.
- b. Within 20 minutes of collection, centrifuge the blood samples at 900xg for 15 minutes to separate plasma.
- c. For each sample collected, pipette duplicate aliquots of plasma, 2 ml each, in polypropylene cryovials (Nunc). Aliquot 1 is the sample and aliquot 2 is the duplicate.
- d. Aliquots are to be frozen and stored at -20°C to -70°C or lower until specimens are shipped to TG Therapeutics. All samples must be shipped within 14 days following collection for further storage and/or analysis.
- e. Specimens can be batched for shipment once all samples have been collected for a patient within 14 days of being collected.

12.10.3 PK Sample Shipping

- a. Samples may be stored at the site for up to 14 days. Samples are to be shipped overnight in sufficient dry ice to keep samples frozen.
- b. One aliquot from each sample will be shipped and the duplicate samples can be sent once TG Therapeutics verifies they have received the first aliquot. Again, all samples must be shipped within 14 days.
- c. Do not ship samples and duplicates in the same box. Save the duplicates and ship them after TG Therapeutics has verified they have received the first aliquot.
- d. Place the patient flow sheets in a separate plastic bag and then place in the shipping box.
- e. Please contact TG Therapeutics either by phone or by email before shipping samples. This is to assure that shipments can be received on that day. This is especially important if shipping on Thursday for a Friday delivery.

f. The laboratory is open to receive samples Monday through Friday. **NOTE:** DO NOT ship samples on Fridays or on days prior to holidays.

12.10.4 Immunogenicity

Serum samples will be screened for antibodies against ublituximab and neutralizing antibodies to ublituximab. Serum samples will be collected prior to the infusion of ublituximab and at 2, 30, and 60 days following the end of the infusion. A titer, if any, will be recorded for each sample and correlated with safety and efficacy data. Approximately 4 mL of blood will be collected per sample.

12.11 DIAGNOSIS VS. SIGNS AND SYMPTOMS

All AEs will be recorded individually in the subject's own words (verbatim) unless, in the opinion of the Principal Investigator or designated physician, the AEs constitute components of a recognized condition, disease, or syndrome. In the latter case, the condition, disease, or syndrome will be named rather than each individual sign or symptom. If a constellation of signs and/or symptoms cannot be medically characterized as a single diagnosis or syndrome at the time of reporting, each individual event will be recorded as an AE or SAE as appropriate on the Case Report Form. If a diagnosis is subsequently established, it will be reported as follow-up information is available. If a diagnosis is determined subsequent to the reporting of the constellation of symptoms, the signs/symptoms will be updated to reflect the diagnosis.

12.11.1 Persistent or Recurrent Adverse Events

A persistent AE is one that extends continuously, without resolution, between subject evaluation time points. Such events will be recorded as "persistent" on the Case Report Form. If a persistent AE becomes more severe or lessens in severity, it will be noted as such on the Case Report Form.

A recurrent AE is one that occurs and resolves between subject evaluation time points, and subsequently recurs. All recurrent AEs will be recorded on the Case Report Form as "recurrent".

12.11.2 Abnormal Laboratory Values

Any grade 3 or 4 laboratory abnormalities or any clinically significant grade 1 or 2 hematology or biochemistry laboratory value(s) will be recorded as an AE. If an abnormal laboratory value or vital sign is associated with clinical signs and/or symptoms, the sign or symptom should be reported as an AE, and the associated laboratory value or vital sign will be considered additional information that must be collected on the relevant CRF. If the laboratory abnormality is a sign of a disease or syndrome, only the diagnosis will be recorded the Case Report Form.

12.11.3 Deaths

Deaths that occur during the protocol-specified AE reporting period that are attributed by the investigator for up to 30 days post the dose of trial drug will be recorded on the appropriate trial CRF. All on-trial deaths, regardless of attribution, will be expeditiously reported to the TG Therapeutics and to the Johns Hopkins IRB.

When recording a serious adverse event with an outcome of death, the event or condition that caused or contributed to the fatal outcome will be recorded as the single medical concept on the Adverse Event page of the CRF. If the cause of death is unknown and cannot be ascertained at the time of reporting, "Death NOS" will be recorded on the CRF Adverse Event page.

12.11.4 Hospitalization, Prolonged Hospitalization, or Surgery

Any AE that results in hospitalization of >24 hours or prolonged hospitalization will be documented and reported as an SAE unless specifically instructed otherwise in this protocol.

12.11.5 Pre-Existing Medical Conditions

A pre-existing medical condition is one that is present at the start of the trial. Such conditions will be recorded on the trial's appropriate medical history CRF. A pre-existing medical condition will be recorded as an AE or SAE only if the frequency, severity, or character of the condition worsens during the trial. When recording such events on the appropriate Case Report Form, it is important to convey the concept that the pre-existing condition has changed by including applicable descriptors.

12.11.6 Pregnancy, Abortion, Birth Defects/Congenital Anomalies

Pregnancy, abortion, birth defects, and congenital anomalies are events of special interest, as described below in section 12.11.7.

12.11.7 Protocol-Defined Events of Special Interest

The following are events of special interest, and will be reported expeditiously:

Pregnancy, Abortion, Birth Defects/Congenital Anomalies

If a subject becomes pregnant while enrolled in the trial, TG Therapeutics will be notified expeditiously, regardless of whether or not it meets the criteria for expedited reporting. Abortions (spontaneous, accidental, or therapeutic) will also be reported to TG Therapeutics.

Congenital anomalies/birth defects **always** meet SAE criteria, and will therefore be expeditiously reported as an SAE, using the previously described process for SAE reporting.

Trial Drug Overdose

Symptomatic and non-symptomatic overdose will be reported in the CRF. Any accidental or intentional overdose with the trial treatment that is symptomatic, even if not fulfilling a seriousness criterion, will be reported to TG Therapeutics immediately (within 24 hours) using the corresponding CRF page, and following the same process described for SAEs (see Section 14). If a trial drug overdose occurs, subjects will stop trial drug dosing and be clinically monitored as appropriate, managing symptoms/side effects that may occur.

